10.1.1.2 Individual Stopping Rules

Safety of the participant will remain of primary importance. Any participant who develops documented hypotension (systolic BP>30% fall from baseline systolic BP), neurological compromise (confusion, loss of consciousness), and/or significant hypotension during any stage of the during any administration of the *B. infantis* product will be withdrawn from the study.

10.1.2 Early Discontinuation of Investigational Product(s) / Intervention(s) with continued study participation / follow-up

10.1.2.1 Unscheduled Termination In accordance with the Declaration of Helsinki, patients have the right to withdraw from the study at any time for any reason. Participants may withdraw with or without medical advice. The investigator also has the right to withdraw participants from the study. Participants will be removed from the

study for the following reasons: adverse experience, intercurrent illness or medication that in the judgment of the investigator may place the participant at risk, request of the investigator or participant for administrative or other reasons, protocol violation, determination that the participant is non-compliant or has unreliable behavior. Withdrawal from this study will have no impact on the future care of the participant at the Massachusetts General Hospital or any of its affiliated hospitals or health clinics.

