4.3 Participant Withdrawal Criteria

Participants may be terminated early from the study for the following reasons:

- The participant elects to withdraw consent from all future study activities, including follow-up.
- The participant is "lost to follow-up" (i.e., no further follow-up is possible because attempts to reestablish contact with the participant have failed).
- The participant dies.
- The participant develops a medical condition or is started on new medication(s) not previously mentioned in the list of prohibited medications that, in the opinion of the investigator, may pose additional risks from participation in the study, may interfere with the participant's ability to comply with study requirements or that may impact the quality of the data obtained from the study.
- The participant meets any of the individual stopping rules as delineated in Section 10.1.1.

Participants with early termination from this study will not be replaced.

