6.1.6 Modification or Discontinuation of Investigational Product(s) / Intervention Material(s)

The parents may withdraw their infant from the study at any time by notifying the study team. Participants may be withdrawn from the study by the investigator if study procedures have not been followed or if the investigator determines the participant is not able to safely continue with the study due to an adverse event or other health-related issue. If greater or equal to 20 percent drop-out occurs, infants may be replaced to assure adequate statistical power.

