9.2.2 Study Participant Populations

Randomization Approximately fifty (50) infants will be randomized in a 1:1 ratio to treatment probiotic or placebo. Randomization will occur immediately after all baseline period tasks have been confirmed to be completed and provide acceptable data.

Populations for Analyses The modified Intent to Treat (mITT) population will include all infants who are randomized and receive at least one supplementation. The Per Protocol (PP) population will include all randomized participants who do not have major protocol deviations. Major protocol deviations will be defined prior to unblinding of the data. Analysis on primary and secondary objectives will be completed based on the mITT population and the PP population; analysis on the exploratory objectives (perception of treatment) will be completed based on the mITT population.

Descriptive Statistics Descriptive statistics (mean, median, and standard deviation, minimum and maximum) of the quantitative variables will be summarized using number of subjects (n). The qualitative variables will be summarized using counts and percentages. All summaries will be presented by treatment group and time point (where relevant).

All CRF and laboratory data will be analyzed. Comparisons between treatment groups will be performed using Fisher's exact test or Pearson's Chi-Square test for categorical data and one-way ANOVA with Tukey's post hoc comparisons for individual timepoints or two-way repeated measures ANOVA for all timepoints for continuous data. Mean and standard deviations for certain groups and timepoints will be used as estimates in power calculations for future studies. Missing data will not be imputed in this study.

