10.1.3 Follow-up after early study termination

Participants who are prematurely terminated from the study will be followed to monitor safety for a minimum of 30 days or until resolution of the disqualifying event whichever is longer or until the Independent Study Monitor and the Principal Investigator determine that the follow-up is complete.

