There is no risk for possible anaphylaxis with our study agent INF108F and placebo. Epinephrine auto injectors and diphenhydramine will not be needed. Potential gastrointestinal adverse effects might occur, including abdominal discomfort and changes of stool frequency and consistency. We will stop administering the study agent if any of adverse events occur and we will treat the symptoms accordingly.

The same protocol will be recommended when signs/symptoms of acute gastrointestinal infection occur. An adverse event will be followed until any of the following takes place: a) it is resolved, b) participant is stable, c) a minimum of 30 days after participant is terminated from the study and the Independent Safety Monitor and the

Principal Investigator determine that follow-up is complete. If an abnormal value or result is determined by the investigator to be clinically significant, it must be recorded as an adverse event on the appropriate laboratory evaluation form(s).

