10.3.2 Reporting Protocol Deviations

Upon determination that a protocol deviation has occurred, the study staff will a) notify the Principal Investigator, b) notify the Infinant Health Project Manager (refer to investigator's signature page for contact information) and c) will complete the Protocol Deviation form. Infinant Health may request discussion with the Principal Investigator and the Independent Safety Monitor to determine the effect of the protocol deviation on the study participant and his/her further study participation, the effect of the protocol deviation on the overall study and corrective actions. The Principal Investigator will complete and sign the Protocol Deviation form and submit it to Infinant's Medical Officer and Project Manager, to the Independent Safety Monitor and to the site IRB, per IRB regulations. Major protocol deviations will be reported to the ISM and Infinant's Medical Officer.

All study staff be educated about the adverse event reporting policy and will be instructed to notify an investigator if an event occurs.

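### Section 10.1.2.1 takes non-compliant infants out of the study, against its own heading and other sections, and no section provides Day 28 sampling after removal

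*Combined protocol and SAP*

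**What the plan says.** The heading of Section 10.1.2 reads "Early Discontinuation of Investigational Product(s) / Intervention(s) with continued study participation / follow-up". The only text beneath it, 10.1.2.1, gives the investigator a right to withdraw infants. It then states, in mandatory form, that participants are removed from the study for a list of reasons. The list includes adverse experience, intercurrent illness and "protocol violation, determination that the participant is non-compliant or has unreliable behavior". It does not describe stopping product while staying in the study.

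Other sections read differently:

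- Section 6.1.6, with the same sentence in 6.5.2: "Participants may be withdrawn from the study by the investigator if study procedures have not been followed".
- Section 10.3.2 provides for a possible discussion after a deviation "to determine the effect of the protocol deviation on the study participant and his/her further study participation".
- Section 4.3: "Participants may be terminated early from the study for the following reasons". Its list does not name protocol violation or non-compliance as grounds.
- Section 10.2.2.4, on adverse events: "We will stop administering the study agent if any of adverse events occur and we will treat the symptoms accordingly".

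After removal, Section 10.1.3 states: "Participants who are prematurely terminated from the study will be followed to monitor safety for a minimum of 30 days". No stool sample, hemoccult card or log is mentioned there.

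On analysis, Section 9.2.2 says: "The modified Intent to Treat (mITT) population will include all infants who are randomized and receive at least one supplementation". PP leaves out infants with major protocol deviations, and missing data are not imputed. Section 9.2.3 compares the arms on microbiome change from baseline to Day 28 with a Wilcoxon rank sum test.

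**The concern.** Non-compliance and protocol violations arise after randomization. If they end an infant's participation, the Day 28 comparison is made among infants selected by what happened after allocation, and the mITT label no longer describes who contributes data.

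The grounds for removal could well be related to outcome. Section 6.2.2 prohibits infant antibiotics and majority formula feeding, so either could be recorded as a violation. Section 1.1 names antibiotic exposure and breastfeeding among the influences on the infant microbiome, which is the primary endpoint. These links do not show that loss differs by arm, but they make it unsafe to assume that removal is unrelated to outcome.

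The mandatory wording also has a practical edge. Section 10.3.1.2 gives, as an example of a major deviation, an infant who met withdrawal criteria and was kept in. If 10.1.2.1 counts as withdrawal criteria, a site that uses the discretion in 6.1.6 to retain a non-compliant infant could be recorded as committing a major deviation.

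**Working it through.** **1. Which rule applies**

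| Section | Force | Ground | What ends |
|---|---|---|---|
| 10.1.2 heading | – | – | product only |
| 10.1.2.1 | mandatory | violation, non-compliance, unreliable behavior, others | study |
| 6.1.6, 6.5.2 | optional | procedures not followed | study |
| 10.3.2 | case by case | deviation | open |
| 4.3 | optional | these grounds not listed | study |
| 10.2.2.4 | – | adverse events | product |

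The direct conflict is between 10.1.2.1 and 6.1.6, 6.5.2 and 10.3.2, and with its own heading. Section 4.3 differs only in wording and by omission.

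**2. What happens to the Day 28 value**

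Under the mandatory or the optional wording, withdrawal is from the study. The stated follow-up is for safety. An infant who has had one supplementation is in mITT, but with no Day 28 sample and no imputation contributes nothing to the baseline-to-Day-28 test. Section 10.3.1.2 equates protocol violation with major deviation, and major deviation defines exclusion from PP. Removal for violation therefore takes out of the mITT comparison the same infants that PP excludes.

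Sections 6.3.3.1 and 6.3.3.4 bring samples to the site only at Day 7 and Day 28. For an infant removed between those visits, no section provides for retrieving samples still at home.

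**3. The plan's own figures (Section 9.1.1)**

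100 × (1 − 0.50) = 50 randomized; 50 × (1 − 0.20) = 40 completing. These reproduce. At 1:1 allocation that is 25 per arm, with 5 lost per arm if losses are even.

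**4. Information recoverable**

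Let k of the 5 losses per arm be investigator removals. The documents do not give k, so the whole range is shown. Full data give 25 × 25 = 625 active–placebo pairs and completers give 20 × 20 = 400, so 225 are lost. Keeping the k infants to Day 28 recovers (20 + k)² − 400 pairs. For a binary Day 28 endpoint with all 25 per arm in the denominator, k missing leaves each arm's percentage known to within k/25, so the difference is undetermined over 2k/25.

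| k per arm | Pairs recovered | Binary range (percentage points) |
|---|---|---|
| 0 | 0 | 0 |
| 1 | 41 | 8 |
| 2 | 84 | 16 |
| 3 | 129 | 24 |
| 4 | 176 | 32 |
| 5 | 225 | 40 |

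**5. Error rate with no true effect**

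This is a simulation under assumed scenarios: 40,000 trials, 25 v 25 normal outcomes, k removed per arm, two-sided 5% Wilcoxon test (normal approximation with continuity correction). Monte Carlo standard error near 5% is √(0.05 × 0.95 / 40,000) ≈ 0.001.

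| Removal | k=1 | 2 | 3 | 4 | 5 |
|---|---|---|---|---|---|
| Random in both arms | 0.049 | 0.048 | 0.049 | 0.050 | 0.048 |
| Both arms, from their lowest 12 of 25 | 0.046 | 0.043 | 0.044 | 0.044 | 0.045 |
| Active from its lowest 12, placebo at random | 0.049 | 0.053 | 0.060 | 0.075 | 0.094 |

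In the third row, the expected chance that an active infant outranks a placebo infant moves from 0.50 to 0.51, 0.52, 0.53 (0.535 before rounding), 0.55 and 0.56. In the first two rows it stays at 0.50.

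**The case against.** The other side has four arguments.

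*Practice is already discretionary.* 10.1.2.1 itself speaks of an investigator's right, non-compliance needs a determination, and 6.1.6, 6.5.2 and 10.3.2 all leave room for judgment. This stands: a reader might infer that removal is a settled mandatory rule, and the documents do not support that. Discretion does not close the gap, though, because an infant withdrawn at discretion also leaves the study with no Day 28 sampling provided.

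*The analysis populations imply that deviators are retained.* Defining PP separately from mITT would mean little if every violator had gone before Day 28. That is a fair reading of intent, but it supplies no procedure for collecting the sample. Adverse events are in a similar position: 10.2.2.4 stops the agent, while 10.1.2.1 lists adverse experience as a reason to leave the study.

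*The bias is hypothetical.* A reader might take the 0.094 figure to mean that the trial's error rate is nearly doubled. The documents do not support that. It needs all 10 planned losses to be investigator removals, and removal tied to outcome in one arm only. Nothing shows such selection, participants and staff are blinded (Section 3), and at k=1 or 2 even this scenario gives 0.049 or 0.053.

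*The gain may be small.* Parents collect the stool, cards and logs. Families removed for not doing so may not supply Day 28 samples either. Product lasts only 14 days, so for a violation on Days 15–28 there is nothing left to stop. Both points stand. They limit what is recovered, and for the later period they mean the rule must say plainly that the infant stays in the study.

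**Conclusion.** The point holds as an inconsistency with a practical gap behind it, and should be fixed. 10.1.2.1 conflicts with its heading, with 6.1.6 and 6.5.2, and with 10.3.2. Under either wording, an infant who belongs to mITT can leave without a Day 28 value, so the primary comparison becomes available-case and moves towards PP.

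The size is unknown because the documents do not say what share of the 20% drop-out is investigator removal. The figures above assume even loss between arms, and the simulation scenarios are assumptions. If removals are few, unrelated to outcome, or similarly selective in both arms, the error rate stays at or below about 5%.

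Two further inferences go too far. Section 4.3 does not flatly contradict 10.1.2.1, since its optional wording governs a list that omits these grounds. Nor does the plan forbid Day 28 stool after removal; it simply does not provide for it. Confidence is medium.

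**What to change.** - In 10.1.2.1, 6.1.6 and 6.5.2, make non-compliance, protocol violation and adverse events that are not safety-critical grounds at most for stopping product (Days 1–14), and never by themselves grounds for leaving the study.
- Continue the scheduled stool samples, hemoccult cards and logs to Day 28 where the family is willing, unless consent is withdrawn or safety prevents it. Retrieve samples already held at home.
- Keep these infants in mITT as randomized, and exclude major deviators only from PP.
- For binary Day 28 endpoints, pre-specify a sensitivity analysis that counts missing as not cleared.
- Do not carry an on-product stool sample forward for the primary comparison. A sample from Days 1–14 would stand in for one due 14 days after the last planned dose (28 − 14), and could credit the active arm with colonization on product rather than persistence.

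The cost is a short amendment. Kits, cards, logs and the Day 7, 14 and 28 visits already exist, and safety contact after removal is already planned. The downside is slightly more data collection and some off-product data in the estimate. Families who have stopped following procedures, withdrawn consent or been lost may not be recovered.

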10.1.3 Follow-up after early study termination

Participants who are prematurely terminated from the study will be followed to monitor safety for a minimum of 30 days or until resolution of the disqualifying event whichever is longer or until the Independent Study Monitor and the Principal Investigator determine that the follow-up is complete.

10.1.4 Participant Replacement

Participants who are permanently discontinued from the study will not be replaced.

10.2 ADVERSE EVENTS

This section defines the types of adverse events and outlines the procedures for appropriately collecting, grading, recording, and reporting them. Information in this section complies with ICH Guideline E2A: Clinical Safety Data Management: Definitions and Standards for Expedited Reporting and ICH E6: Guideline for Good Clinical Practice, and applies the standards set forth in the National Cancer Institute (NCI), Common Terminology Criteria for Adverse Events version 4.0. These criteria have been reviewed by the study investigators and have been determined appropriate for this study population.

10.2.1 Definitions

10.2.1.1 Adverse Events An adverse event (AE) is any occurrence or worsening of an undesirable or unintended sign, symptom, laboratory finding, or disease that is experienced during participation in the trial. An AE can therefore be any unfavorable and unintended sign (including an abnormal laboratory finding), symptom, or disease temporarily associated with the use of a medicinal (investigational) Study Agent(s) whether related to the medicinal (investigational) Study Agent(s) or not. Any medical condition that is present at the time that the participant is screened will be considered as baseline and not recorded as an AE. However, if the condition deteriorates or changes in severity at any time during the study it will be recorded and reported as an AE.

10.2.1.2 Suspected Adverse Reaction and Adverse Reaction Suspected adverse reaction (SAR) means any adverse event for which there is a reasonable possibility that the drug caused the adverse event. For the purposes of safety reporting, “reasonable possibility” means there is evidence to suggest a causal relationship between the drug and the adverse event.

An adverse reaction (AR) means any adverse event caused by a drug. Adverse reactions are a subset of all suspected adverse reactions for which there is reason to conclude that the drug caused the event. A suspected

adverse reaction implies a lesser degree of certainty about causality than adverse reaction, which means any adverse event caused by a drug.

10.2.1.3 Adverse Events Associated with Study Procedures The following clinical situations, when associated with study procedures, are defined as adverse events and will be recorded on the AE CRF. These situations do not limit the principal investigator from recording and reporting any other events as AEs, associated or not with these procedures.

10.2.1.4 Serious Adverse Event (SAE) An AE or SAR (including AR) is considered serious if, in the view of the investigator, it results in any of the following outcomes (21 CFR 312.32):

- Death. A death that occurs during the study or that comes to the attention of the investigator during the protocol-defined follow-up.
- A life-threatening event. A life-threatening event is any adverse experience that, in the view of the investigator, places the study participant at immediate risk of death from the reaction as it occurred. It does not include an adverse event or suspected adverse reaction that, had it occurred in a more severe form, might have caused death.
- An inpatient hospitalization or prolongation of existing hospitalization.
- Persistent or significant disability/incapacity or substantial disruption of the ability to conduct normal life functions.
- An important medical event that may not result in death, be life threatening, or require hospitalization may be considered an SAE when, based on appropriate medical judgment, it may jeopardize the participant and may require medical or surgical intervention to prevent one of the outcomes listed above.
- Congenital anomaly or birth defect.

Regardless of the relationship of the adverse event to the study, the event will be reported per Section 8.2.2.3 as an SAE if it meets any of the above definitions.

10.2.1.5 Unexpected Adverse Event An AE or SAR (including AR) is considered “unexpected” if it is not consistent with the risk information described in the study protocol.

10.2.2 Collecting, Recording and Managing Adverse Events

10.2.2.1 Identifying Adverse Events Any adverse event that occurs from the moment the participant has signed the consent form will be recorded and is reportable. Adverse events will be reported until the participant has completed the long-term follow-up phase.

Adverse events may be discovered through any of these methods:

- Observing the participant.
- Questioning the participant with standardized questions/procedures.
- Receiving an unsolicited complaint from the participant.
- An abnormal value or result from a clinical or laboratory evaluation (e.g., a radiograph, an ultrasound, or an electrocardiogram) can also indicate an adverse event.

Adverse events will be captured as follows: (1) every occurrence as per the NCI-CTCAE criteria, (2) for protocol-specific adverse events (Section 10.2.1.3) or (3) when determined to be clinically significant by the Principal Investigator.

All adverse events occurring during or within 24 hours of the study procedures will be reported as an adverse event.

10.2.2.2 Recording AEs Throughout the study, all identified adverse events (serious and non-serious) will be recorded on all appropriate source document and adverse event case report forms regardless of their severity or relation to the study.

A complete description of all adverse events will include event description, time of onset, investigator assessment of severity, relationship to study agent(s) or procedures/intervention(s), time of resolution/stabilization of the event, expectedness, determination of whether the AE qualifies as a SAE, and action taken. A change in the severity of the AE will also be documented. The PI will document assessment of severity and relationship on the source documents or the on the CRF.

10.2.2.3 Recording SAEs Serious adverse events will be recorded on the serious adverse event case report form and will include a narrative of the event signed and dated by the Principal Investigator and the Independent Safety Monitor.

10.2.2.4 Managing Adverse Events The site investigator must apply his or her clinical judgment as to whether an AE is of sufficient severity to require that the participant immediately be removed from further treatment under the protocol. The investigator must institute any necessary medical therapy to protect a participant from any immediate risk.

There is no risk for possible anaphylaxis with our study agent INF108F and placebo. Epinephrine auto injectors and diphenhydramine will not be needed. Potential gastrointestinal adverse effects might occur, including abdominal discomfort and changes of stool frequency and consistency. We will stop administering the study agent if any of adverse events occur and we will treat the symptoms accordingly.

The same protocol will be recommended when signs/symptoms of acute gastrointestinal infection occur. An adverse event will be followed until any of the following takes place: a) it is resolved, b) participant is stable, c) a minimum of 30 days after participant is terminated from the study and the Independent Safety Monitor and the

Principal Investigator determine that follow-up is complete. If an abnormal value or result is determined by the investigator to be clinically significant, it must be recorded as an adverse event on the appropriate laboratory evaluation form(s).

